The Mesh-RTL Project for Prevention of Incisional Hernia. Clinical Trial of Non-inferiority to Compare Two Aponeurotic Closure Techniques in Midline Laparotomy in Patients With Elevated Risk for Hernia.

Sponsor: Hospital Regional de Alta Especialidad del Bajío
Responsible Party: Principal Investigator
Investigator: [name] [[name]]
Official Title: Master in clinical research
Affiliation: Hospital Regional de Alta Especialidad del Bajío
Collaborators: [name]
[name]

Approval Number: CI/HRAEB/2018/008

Board Name: Comité de ética en investigación

Board Affiliation: CNBCEI-11-CEI-004-20170731

Friday October 18th 2019

Introduction:

The laparotomy is a surgical incision into the abdomen cavity performed to examine the abdominal and retroperitoneal organs. It is classified according to the medical indication: exploratory, therapeutic, stagemaker, and recently added "damage-control" laparotomy.

There exists so many ways to access the abdominal cavity, usually in relation with the organ or structure to treat; being classified in midline laparotomy, paramedian, transversal, oblique, abdominal-thoracic, etc.

Either an emergency or scheduled procedure, the more usual and functional continues being the midline laparotomy, since it allows a broader and faster approach, with less bleeding and easily to extend if it becomes necessary.

Both the evisceration/eventration and the hernia are considered the most frequent complication of the midline laparotomy with a high morbidity and mortality related. Conditions that will require a second intervention, in Mexico represent the seventh cause of elective surgery and fourth cause of emergency procedures.

So far only the use of the mesh has proven useful in reducing this complication. Our group published in 2016 a clinical trial where it showed that the technique is safe and effective to reduce the presence of incisional hernia, however the use of the mesh brings with it problems such as cost, possibility and use in contaminated cavities and postoperative pain. Therefore, the use of the RTL technique as an alternative means to this will help to have one more option for the management of patients with a high risk of incisional hernia.

Problem Statement:

Does the RTL closing technique in the midline laparotomy has the same incident of herniation than the close with supraaponeurotic mesh in patient with elevated risk?

Justification

The presence of postincisional hernia need to be considerate as a serious disease, insomuch as it carry on highs rates of morbimortality. The presence of this eventuality is among 0.4-1.2% in elective

surgery and up to 30% in emergency procedures.

It is calculated in de U.S.A. an approximate of 1 million of reinterventions a year to correct this condition, with the respective monetary, time and suffering cost to the patient and the health system.

Given the seriousness, the ultimate global consensus has determinate three main axes to the surgical community to board:

- Identify the relevance of the problem
- Improve the theoretical knowledge and technical capacity in the closing of the abdominal wall
- Implement prophylactic measures in the patients, especially in those with elevated risk.

With the present study we aim to contribute to this global recommendations, comparing two closing techniques of the abdominal wall after a midline laparotomy in patients with elevated risk of herniation. Both techniques are proved safe and useful in other studies, with no comparison to date.

Demonstrate that the use of RTL technique has a similar incidence of herniation than the mesh, in an attempt to prevent postincisional hernias after a midline laparotomy, will bring to the surgical community a cheaper and practical alternative to the mesh.

Objectives:

General:

To determinate if the incidence of post-incisional hernia in patients with high risk after a midline laparotomy are similar between the closure of the abdominal wall with the RTL technique and the supraaponeurotic mesh closure reinforcement.

Specifics:

- To identify the patients with high risk using de validated HERNIA-Project Score.
- To determinate the incidence of post-incisional hernia after one year of the initial midline laparotomy.
- To compare the incidence of post-incisional hernia between the two groups.
- To describe the complications related to each closure technique.

Hypothesis:

Ho Hypothesis:

There is no difference in the incidence of post-incisional hernia between the RTL technique and the reinforcement with supraaponeurotic mesh closure wall.

H1 Hypothesis:

There is difference in the incidence of post-incisional hernia between the RTL technique and the reinforcement with supraaponeurotic mesh closure wall.

Sample size:

The sample size was calculated according to the formula published by Bouemn et all 2015, and based on the results of Kholer and collaborators 2019, where they found in which a percentage of

success was estimated with the standard treatment of 18.5% compared to the experimental management of 7.2%, with a margin of no less than 3%, with an alpha for a tail of 0.05%, and a beta of 20 %, with a percentage of estimated losses of approximately 10%, a total of 195 patients per group was obtained.

Statistical analysis Data are presented as frequency and percentage, comparisons between groups were using the χ^2 test for binary data or Fisher's exact test. Continuous variables are presented as median and range interquartile range and were compared using the Mann-Whitney U-test or t student test if they meet normal criteria. p-Values of less than 0.05 were considered significant. Statistical analyses were performed with SPSS version 25.0.0. Analysis by intention to treat was used.

Study Type:	Interventional
Primary Purpose:	Treatment
Study Phase:	Phase 4
Interventional Study Model:	Parallel Assignment
	Clinical trial of non-inferiority
Number of Arms:	2
Masking:	Triple (Participant, Care Provider, Investigator)
Allocation:	Randomized
Enrollment:	390 [Anticipated]

Primary Outcome Measure:

1. Incisional Hernia

any abdominal wall gap with or without bulge in the area of a postoperative scar perceptible or palpable by clinical examination

[Time Frame: 12 and 24 months]

Secondary Outcome Measures:

2. postoperative complications

an undesirable and unintended result of an operation affecting the patient that occurs as a direct result of the operation. Haematoma, Facial dehiscence, mesh removal, ileus, reinterventions, re-admissions and death

[Time Frame: 1 month, 1 and 2 years]

Elegibility:

Minimum Age:	18 Years
Maximum Age:	70 Years
Sex:	All
Gender Based:	No

Accepts Healthy Volunteers: Yes

Criteria:

Inclusion Criteria:

- Patients older than 18 years undergoing midline laparotomy, independently of diagnostic or condition, elective or emergency surgery
- Patients with a score equal or greater than 7 of the hernia score
- Patients who accept to participate and sign the informed consent

Exclusion Criteria:

- Patients managed with open abdomen or with the impossibility of close the wall
- Patients who had a previous incisional hernia or patients who are participating in another trial
- Patients with a life expectative less than 12 months
- Pregnant patients Patients with the antecedent of rejection of prosthetic material

Revised Hernia Score.

$$\text{Revised HERNIA score} = 1 \times (\text{BMI} \geq 25 \text{ kg/m}^2) + (1 \text{ COPD}) + (5 \times \text{extended laparoscopy}) + (6 \times \text{laparotomy}) + (3 \times \text{earlier abdominal operation})$$

The revised HERNIA score was developed and low risk was assigned 0 to 6.9 points, medium risk was assigned 7.0 to 9 points, and high risk was assigned ≥ 9 points.

[figure not shown]
Arms and interventions:

Active Comparator: Onlay Mesh Reinforcement group

The midline fascia was closed with running, slowly absorbable sutures (PDS 1-0) with a recommended suture length to wound length ratio of 4:1. An anterior plane with a width of about 8 cm was created between the anterior fascia and the subcutis. A Lightweight polypropylene mesh was used and placed on the anterior rectus fascia with an overlap of 3 cm. The mesh was fitted in the dissected space and it was fixed with PDS 2-0 suture. Fixing points are placed taking the mesh and the anterior fascia of the rectus muscle, at a distance of 3 cm between each point until completing its circumference.

Experimental: RTL reinforcement group

The RTL suture is placed parallel at a distance of 0.5 cm from the fascial margin. Ideally the thread should lie between the anterior and the posterior rectus muscle sheath; there should be no contact with the rectus muscle. A nonabsorbable monofilament polypropylene thread and a 65-mm $\frac{1}{2}$ needle are used. Around this longitudinal thread, the continuous suture for fascial closure is introduced immediately lateral to the thread; with running, slowly absorbable sutures (PDS 1-0) with a recommended suture length to wound length ratio of 4:1. An anterior plane with a width of about 8 cm was created between the anterior fascia and the subcutis.

References

- Shell DH 4th, de la Torre J, Andrades P, Vasconez LO. Open repair of ventral incisional hernias. Surg Clin North Am. 2008 Feb;88(1):61-83, viii. doi: 10.1016/j.suc.2007.10.008. Review. PubMed ID: 18267162

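### The trial is labelled non-inferiority with a 3% margin, but its hypotheses and only hernia test contain no margin, so non-inferiority follows only if RTL is significantly better

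*Combined protocol and SAP*

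**What the plan says.** The title reads "Clinical Trial of Non-inferiority to Compare Two Aponeurotic Closure Techniques in Midline Laparotomy" and the design table repeats "Clinical trial of non-inferiority". The Sample size section works "with a margin of no less than 3%, with an alpha for a tail of 0.05" (printed with a percent sign), 80% power and about 10% losses, and arrives at 195 per group. Its planning rates are introduced thus: "success was estimated with the standard treatment of 18.5% compared to the experimental management of 7.2" percent.

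The Hypothesis section has no margin. The null is "There is no difference in the incidence of post-incisional hernia between the RTL technique and the reinforcement with supraaponeurotic mesh closure wall"; the alternative is "There is difference in the incidence of post-incisional hernia between the RTL technique and the reinforcement with supraaponeurotic mesh closure wall".

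The Statistical analysis paragraph compares groups with the chi-square "test for binary data or Fisher's exact test", and "p-Values of less than 0.05 were considered significant". It mentions no confidence interval for the difference in hernia incidence, no margin and no decision rule. The Problem Statement, Justification and general objective all aim to show that RTL has the same or a similar incidence to mesh.

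**The concern.** A test of equality can reject sameness; it cannot establish it. With these hypotheses the plan has one valid route to non-inferiority: RTL significantly better than mesh. If the two rates are close, which is what the trial hopes to show, no valid conclusion is available.

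The document does not say that p of 0.05 or more will be read as similarity. But with a null of no difference and an aim of similarity, that is the only reading left that would deliver the stated aim, and it would accept RTL at excess hernia rates well beyond the trial's own margin.

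**Working it through.** **Inputs.** From the Sample size section: rates 18.5% and 7.2%, margin 3% (read as 3 percentage points), one-tailed alpha (printed 0.05%, read as 5%), power 80%, losses 10%, 195 per group. Evaluable after losses: 195 × 0.9 ≈ 175. From Statistical analysis: chi-square at p < 0.05, taken as two-sided and uncorrected.

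**The plan's own figure.** With unpooled variance:

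- Variance sum: 0.185×0.815 + 0.072×0.928 = 0.2176
- (1.645 + 0.842)² = 6.183 (unrounded normal quantiles)
- Margin subtracted: 6.183 × 0.2176 / (0.113 − 0.03)² = **195.3**, matching 195 before losses; 195.3/0.9 = 217 after them
- Margin added: 6.183 × 0.2176 / (0.113 + 0.03)² = **65.8**; 73 after losses

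If the rates are hernia rates, non-inferiority would add the margin, because RTL is assumed 11.3 points better; subtracting it sizes a trial to show superiority by more than 3 points. If they are literally success rates, RTL is assumed 11.3 points worse, beyond the margin. On neither reading is 195 a valid non-inferiority size, so the sample size does not supply the missing rule.

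**What the written test does.** I enumerated all outcomes of two binomials. The comparator is a non-inferiority test that passes when the Newcombe one-sided 95% upper limit for RTL minus mesh is below +3 points. The documents give no clear mesh hernia rate, so both printed figures are used as assumptions (7.2% is printed for the experimental arm).

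With 195 per group:

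| True RTL excess (points) | Chi-square non-significant, mesh 7.2% / 18.5% | Non-inferiority passes, mesh 7.2% / 18.5% |
|---|---|---|
| +3 | 82% / 88.5% | 5.0% / 5.1% |
| +5 | 61% / 77% | 1.0% / 1.7% |
| +6 | 49% / 70% | 0.4% / 0.9% |
| +8 | 28% / 53% | under 1% |
| +10 | 13% / 35% | under 1% |

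Non-significance falls to 50% at an excess of +5.9 or +8.3 points (+6.4 or +8.8 with 175 per group). Fisher's test is more permissive: 68% or 81% at +5.

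**In counts.**

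- With 14/195 mesh hernias, chi-square stays non-significant up to 25 on RTL; non-inferiority allows at most 11. With 36/195, the figures are 52 and 29.
- RTL 24/195 against mesh 14/195: p = 0.088, upper limit +10.2 points. RTL 50/195 against 36/195: p = 0.087, upper limit +14.0 points.
- The reverse error also occurs. RTL 13/175 against mesh 20/175: p = 0.20, yet the upper limit is +1.2 points, so true non-inferiority would go unclaimed.

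**Where the written test does not mislead.** If true hernia rates are mesh 18.5% and RTL 7.2%, chi-square significantly favours RTL 93% of the time (90% with 175). Every result significantly favouring RTL also meets the margin: the largest upper limit among them, at 195 per group, is −0.3 points. At equal true rates, such a result occurs about 2.5% of the time.

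**The case against.** Three points deserve weight.

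First, the document never says that non-significance will be interpreted as similarity, so the acceptance rates above measure a misreading that is not planned. That is correct. They are conditional illustrations, and they also rest on assumed mesh rates. What does not depend on them is that no rule exists for the claim the trial is designed to make.

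Second, if the planning rates are hernia rates and prove true, the written test works through superiority. That is also correct, but superiority is not the stated aim, and the plan fails precisely when the techniques perform alike.

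Third, the sample size cites a non-inferiority method, and 195 does come from a formula of that form. The formula squares the distance from the margin, so it returns 195.3 even when the planning alternative lies on the wrong side. The fair description is that its inputs or direction are inconsistent, and the remedy depends on what the rates mean. This is secondary to the missing decision rule and does not weaken it.

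**Conclusion.** The concern holds and should be fixed before analysis. The design label and margin belong to non-inferiority; the hypotheses and test belong to a comparison for difference. As written, non-inferiority can be concluded only when RTL is significantly better. Were non-significance taken as similarity, RTL would be accepted more often than not at true excesses from 3 points up to about 5.9 (mesh 7.2%) or 8.3 (mesh 18.5%). Beyond those, chi-square more often than not finds RTL worse, so the risk is confined to modest excesses. The figures assume a 3-point absolute margin, 5% one-sided alpha, 195 per group and the two mesh rates shown. The inconsistency itself needs none of these assumptions.

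**What to change.** - Restate the hypotheses as H0: p(RTL) − p(mesh) ≥ 3 percentage points; H1: less than 3 points.
- Name one score-type interval for the risk difference (Newcombe or Farrington–Manning; pass rates are practically the same here). Claim non-inferiority only if the one-sided 95% upper limit is below +3 points.
- Confirm that the margin means percentage points of hernia incidence, that the printed one-tailed 0.05% means 5%, and whether 18.5% and 7.2% are hernia rates. Until then this rule is provisional.
- Name one time point for the decision, since the primary outcome lists both 12 and 24 months, and say how the roughly 10% missing hernia outcomes enter the test.
- State that a non-significant chi-square is not evidence of similarity, and keep chi-square or Fisher for secondary comparisons.

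The wording costs a few sentences and no new data. The real cost is power. At equal true rates the rule passes about 30% (at 7.2%) or 19% (at 18.5%) of the time with 195 per group, and 28% or 18% with 175. For 80% power at equal rates, n = 6.183 × 2p(1−p)/0.03² gives 918 (p = 0.072) or 2,072 (p = 0.185) evaluable per group. If the true hernia rates are 18.5% on mesh and 7.2% on RTL, it passes over 99% of the time. The plan must therefore say which true difference it relies on.

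### The 195 per group matches a calculation for RTL beating mesh by more than 3 points; if incidence is similar, non-inferiority power is about 18–29%, not 80%

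*Combined protocol and SAP*

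**What the plan says.** The title and the study-type table describe the design as "Clinical trial of non-inferiority". The general objective is to find out whether the hernia incidences "are similar between the closure of the abdominal wall with the RTL technique and the supraaponeurotic mesh closure reinforcement". The Problem Statement and Justification express the same aim.

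The Sample size section starts from a different picture: "success was estimated with the standard treatment of 18.5% compared to the experimental management of 7.2%, with a margin of no less than 3" per cent. It continues "with an alpha for a tail of 0.05", printed with a percent sign, gives a beta of 20%, and ends "with a percentage of estimated losses of approximately 10%, a total of 195 patients per group was obtained". Enrolment is 390. The formula is cited but not written out, and no power is given for equal or similar rates.

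The null hypothesis is that "There is no difference in the incidence of post-incisional hernia between the RTL technique and the reinforcement with supraaponeurotic mesh closure wall". For binary outcomes the Statistical analysis paragraph offers the χ² "test for binary data or Fisher's exact test", with p below 0.05 as significant. It does not compare a confidence limit with the margin.

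**The concern.** A non-inferiority calculation measures the distance from the expected true difference to the margin on the unfavourable side. If RTL is expected to have the lower hernia rate, the margin adds to the expected difference; if the techniques are expected to be equal, the margin is the whole distance. The figure of 195 appears to come from subtracting the margin from a large favourable difference, which answers another question.

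If so, the stated beta of 20% does not describe the trial's chance of reaching its own objective. At the rates quoted in the plan, similar true incidence would most likely give an inconclusive result. Because the analysis tests only for a difference, a non-significant p-value could then be misread as evidence of similarity.

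**Working it through.** **Inputs.** From Sample size: rates 0.185 and 0.072, margin 0.03, one-sided alpha, 80% power, 10% losses, 195 per group. Two readings are assumed: alpha printed as 0.05% means 5% (the analysis paragraph uses p < 0.05), and the margin is in absolute points. Losses leave 195 × 0.9 = 175.5, taken as 175 per arm.

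**Reproducing 195.** Formula: n = (z_α + z_0.80)² × [p₁(1−p₁) + p₂(1−p₂)] / d², with z values 1.645 and 0.842.

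- Variance term: 0.185 × 0.815 + 0.072 × 0.928 = 0.2176.
- d = 0.113 − 0.03 = 0.083: n = 195.3. This matches before losses; with them it is 217 (÷ 0.9) or 215 (× 1.1).
- d = 0.113 + 0.03 = 0.143, the non-inferiority distance if the rates are hernia incidence: n = 66, or about 73–74 with losses.
- d = 0.113, no margin: n = 105.4.
- Relative margin, 0.03 × 0.185 = 0.00555: n = 96 to 117, or 105 to 129 with losses.
- Alpha literally 0.05% one-sided, d = 0.143: n = 182, or 200–202 with losses.

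**Power at the planned size.** Power = Φ(d/SE − 1.645), where SE is the square root of the summed variances divided by n.

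| True situation | d | 195 per arm | 175 per arm |
|---|---|---|---|
| Showing RTL better by more than 3 points (18.5% v 7.2% hernia) | 0.083 | 80.0% | 76.1% |
| Non-inferiority, RTL 11.3 points better | 0.143 | 99.6% | 99.2% |
| Non-inferiority, rates taken as success, as printed | −0.083 | 0.002% | 0.003% |
| Non-inferiority, both arms 7.2% | 0.03 | 31% | 29% |
| Non-inferiority, both arms 12.85% (midpoint) | 0.03 | 22% | 21% |
| Non-inferiority, both arms 18.5% | 0.03 | 19% | 18% |

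Example, both arms 18.5% at 175: SE = √(2 × 0.185 × 0.815 / 175) = 0.0415; 0.03/0.0415 − 1.645 = −0.92; Φ = 0.178. An exact binomial check of the three equal-rate cases at 175 gives 30%, 21% and 18%.

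**Precision.** For common rates of 7.2% to 18.5%, 1.645 × SE is 4.3 to 6.5 points at 195 and 4.5 to 6.8 at 175. Identical observed rates therefore leave the upper limit above 3 points. They meet the margin only if the common rate is about 3.4% or less (195) or 3.0% or less (175).

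**What 80% would need.** At 175 per arm it needs one of these:

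- a common rate of about 1.3% or less; or
- RTL truly better by 3.1 points if the mesh rate is 7.2% (RTL 4.08%), rising to 6.5 points if the mesh rate is 18.5% (RTL 11.99%).

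With equal rates of 7.2% to 18.5%, 80% needs 918 to 2,072 evaluable per arm, or 1,020 to 2,303 with losses.

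**The case against.** The best counter-argument is that the mechanism is inferred. The 195.3 match requires reading the printed alpha as one hundred times larger and ignoring losses that the text lists as an input. Taking alpha literally at 0.05%, with the margin correctly signed and losses included, gives 200–202, only 5 to 7 above 195. On that reading non-inferiority power is 84% at 195 and 78% at 175, close to the stated 80%. This deserves weight, but it does not give 195, it conflicts with the p < 0.05 criterion, and it leaves only about 1% power if the rates are equal. Two other near matches need an alpha or power that the text does not state: superiority at two-sided 5% and 90% power with losses (about 197–200), and non-inferiority at one-sided 0.025% without losses (199).

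The direction is also not proved. The distance is squared, so 195 arises equally if the figures are success rates and RTL is worse. Nor does the text say that the standard treatment at 18.5% was mesh. Both points stand, and they are reasons for labelling the rates and arms against the source. On neither direction is 80% the non-inferiority power at one-sided 5%.

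Finally, the 18–29% depends on the common rate, which the plan does not give. The Justification reports "The presence of this eventuality is among 0.4-1.2% in elective" surgery and up to 30% in emergencies. At 175 per arm, power is 82% at 1.2% and 15% at 30%. The trial selects patients at elevated risk and admits both elective and emergency surgery, so a rate near 1% is hard to assume without a source.

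**Conclusion.** The concern holds. At one-sided 5% with a 3-point absolute margin, 195 per group corresponds to 80% power for RTL being better than mesh by more than 3 points, before losses (76% after 10% loss). The stated beta of 20% is not the non-inferiority error rate on any of the three readings: an 11.3-point advantage for RTL (99%), the literal success wording (near zero), or similar incidence (18–29% at 175 per arm for common rates of 18.5% down to 7.2%).

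That 195 was obtained in this way is an inference from a close numerical match. The low power under similar rates does not depend on it, since it needs only the sample size, margin, alpha and a common rate. As the objective is similarity, this must be corrected before the stated power is relied on.

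**What to change.** Keep 390 and rewrite the Sample size paragraph:

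1. Label the rates as hernia incidence, checked against the cited source. State alpha as 5% one-sided and the margin as 3 absolute points, with its direction: RTL minus mesh below +3.
2. Give the expected incidence for onlay mesh and for RTL, either equal or with a sourced true difference, and put the margin on the correct side.
3. Replace the beta of 20% with loss-adjusted power (about 18–29% for equal rates of 18.5–7.2% at 175 per arm) and precision (one-sided 95% half-width of about 4.5–6.8 points).
4. State that this power refers to comparing the one-sided 95% upper confidence limit for RTL minus mesh with the margin. Add that comparison to the Statistical analysis paragraph and reword the hypotheses to match.

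Otherwise, describe the calculation as superiority of RTL by more than 3 points, with 80% power for 195 evaluable per arm and 76% after 10% loss. The title and objective would then no longer fit and would need rewording.

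The cost is one rewritten paragraph, one added analysis sentence and reworded hypotheses, with no added patients. If similar rates are assumed, the stated power becomes much less favourable.

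### The non-inferiority margin is worded as a minimum of 3%, without scale or direction, and no hypothesis or planned test uses it

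*Combined protocol and SAP*

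**What the plan says.** The title and the study-model entry describe a non-inferiority trial. The only margin is in the Sample size section: "with a margin of no less than 3%, with an alpha for a tail of 0.05" per cent. The same sentence gives:

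- one-sided alpha, printed as 0.05 with a per cent sign
- "and a beta of 20" per cent
- "success was estimated with the standard treatment of 18.5% compared to the experimental management of 7.2" per cent
- "with a percentage of estimated losses of approximately 10" per cent
- a result of 195 per group, matching the planned enrolment of 390

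No other section adds to this. The general objective asks whether hernia incidences "are similar between the closure of the abdominal wall with the RTL technique and the supraaponeurotic mesh closure reinforcement". Under Hypothesis, the null is no difference and the alternative is a difference. The Statistical analysis paragraph compares binary data by chi-square or Fisher's exact test, with "p-Values of less than 0.05 were considered significant". It gives no confidence limit for the difference and no rule for declaring non-inferiority.

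**The concern.** A non-inferiority conclusion depends on one number fixed in advance: how much worse the new closure may be and still count as acceptable. Here that number is phrased as a lower bound. The text does not say whether it is in percentage points or relative to the mesh rate, or which arm is subtracted from which. No planned test uses it.

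Two things are at stake. First, someone who adopted 5, 8 or 10 points once the hernia rates were known would not contradict the written phrase, and the error rate of a non-inferiority claim is controlled only if the margin is fixed beforehand. Second, with no margin-based rule, the only planned test is one of difference, and a non-significant result could be taken as support for similarity when it is not evidence of non-inferiority.

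**Working it through.** **Inputs, all from the Sample size section:** 18.5% standard, 7.2% experimental, margin 3%, one-sided alpha (5% or 0.05%), power 80%, losses about 10%, 195 per group.

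**1. Reproduce 195.** Use unpooled variance, absolute margin m and observed difference d = 0.185 − 0.072 = 0.113.

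- n = (z_α + z_β)² × [p₁(1−p₁) + p₂(1−p₂)] / (d − m)²
- (1.645 + 0.842)² = 6.183
- Variance sum: 0.185×0.815 + 0.072×0.928 = 0.1508 + 0.0668 = 0.2176
- n = 6.183 × 0.2176 / 0.083² = **195.3**, against 195 stated

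**2. What the match depends on.** Change one element at a time:

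| Change | n per group |
|---|---|
| None (3 points, alpha 5%, margin subtracted, no losses) | 195.3 |
| Margin 5 points | 339 |
| Margin 8 points | 1,235 |
| Margin 10 points | 7,960 |
| Margin 3 points added: 0.113 + 0.03 = 0.143 | 66 |
| One-sided alpha 2.5% | 248 |
| Alpha 0.05% as printed | 540 |
| Pooled variance | 202 |
| Losses included: 196/0.9 or 196×1.1 | 218 or 216 |

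At the stated 80% power, plain superiority formulas do not give 195 either (108 to 154, one- or two-sided, with or without continuity correction). The calculation therefore appears to have used 3 percentage points absolute and alpha of 5%, and to have left out the losses.

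**3. Direction.** The rates are labelled as success but look like hernia rates. If they are hernia rates with RTL lower, a non-inferiority margin would be added to the 11.3-point advantage (66 per group), not subtracted from it. The subtraction that yields 195 is the calculation for showing a benefit larger than 3 points. The arithmetic points to a value and a scale, but it does not supply a usable non-inferiority rule.

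**4. How much the choice of margin matters.** The protocol gives no scenario with equal true rates, so I assume a common rate p and take its two printed rates as the range. With 195 per arm and one-sided 5%:

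- SE = √[2p(1−p)/195], which is 0.0262 at p = 7.2% and 0.0393 at p = 18.5%
- Chance of declaring non-inferiority = Φ(m/SE − 1.645)

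| Margin | p = 7.2% | p = 18.5% |
|---|---|---|
| 3 points | Φ(−0.50) = 31% | Φ(−0.88) = 19% |
| 5 points | Φ(0.27) = 60% | Φ(−0.37) = 35% |
| 8 points | Φ(1.41) = 92% | Φ(0.39) = 65% |
| 10 points | Φ(2.18) = 98.5% | Φ(0.90) = 82% |

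With 175 evaluable per arm (195 less about 10%), the figures are 29% to 18% at 3 points and 98% to 78% at 10.

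**5. Margin the sample size supports.** At equal true rates and 80% power, m = (1.645 + 0.842) × SE, which is 6.5 points at 7.2% and 9.8 points at 18.5%. A 3-point margin would need 6.183 × 2p(1−p)/0.03², which is 918 to 2,072 per arm before losses.

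**The case against.** The strongest reply is that the protocol's own arithmetic identifies the margin. Three absolute points returns 195; 5, 8 and 10 points return 339, 1,235 and 7,960. The prose is visibly translated, and the phrase may be a loose rendering of a non-inferiority margin of 3%. Direction can also be inferred, since RTL is the experimental arm, mesh the active comparator, and the outcome is hernia.

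Most of this stands, and it rules out several stronger readings that a reader might infer:

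- **That the sponsor deliberately chose an open-ended margin, or that wider margins fit the protocol as well as 3 points do.** They fit the phrase but not the 195 per group printed beside it.
- **That a relative margin is a live alternative.** Three per cent of 7.2% to 18.5% is 0.2 to 0.6 points. In the equal-rates formula this needs about 177,000 to 60,500 per arm, which cannot coexist with 390 patients.
- **That this phrase alone removes error control.** The hypotheses and tests use no margin at all, so the absent decision rule contributes at least as much.

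What the reply does not do is bind the analysis. The match requires reading alpha as 5%, omitting the stated losses and subtracting the margin in a direction that does not suit non-inferiority on hernia incidence. No text carries the inferred 3 points into a hypothesis or test.

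**Conclusion.** The point holds as a defect of specification. The plan as written contains no usable non-inferiority threshold: its only margin is phrased as a minimum, without scale or direction, and nothing in the hypotheses or analysis uses it. Three absolute points was probably intended.

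Moving from 3 to 10 points raises the chance of a non-inferiority claim from between 19% and 31% to between 82% and 98.5%. That illustration assumes equal true rates of 7.2% to 18.5%, all 195 per arm evaluable, one-sided 5% and a normal approximation.

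A reader might also call it a false positive whenever RTL passes a wide margin while truly several points worse. That is an error only if 3 points is already taken as the true limit. Under an 8-point margin, a closure 5 points worse is non-inferior by definition. The documents do not support the stronger charge. They support only the statement that the limit is not fixed in the text.

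**What to change.** Replace the margin phrase with:

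> The non-inferiority margin is 3 percentage points on the absolute risk difference in incisional hernia (RTL minus mesh). RTL is declared non-inferior only if the upper limit of the one-sided 95% confidence interval (two-sided 90%) is below +3 points. A non-significant chi-square or Fisher test is not evidence of non-inferiority.

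Also:

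- Restate the hypotheses to match: null, RTL minus mesh is 3 points or more; alternative, it is less than 3 points.
- Correct alpha from 0.05% to 5%, and give the reason for choosing 3 points.
- Date the correction before any comparison by arm.

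The change takes a few sentences and no new data. The cost is that the sponsor gives up the freedom to use a wider margin. It must also acknowledge that, at equal true rates, 195 per arm gives at most about 31% power for 3 points. That shortfall exists whether or not the margin is written down, and is no reason to leave it open.
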